8.5. Treatment Period (Visits 6 to 15)

During the treatment period, the following procedures will be completed at each visit for each participant:

- Obtain interval medical history (with special emphasis on BP control and CVD events).
- Review of concomitant medications and AEs.
- Review RASB and BP therapy.
- Measure height, weight, and vital signs according to the schedule outlined in Figure 1
- Inspect for skin rash.
- Conduct a physical exam (Visit 11).
- Perform ECG according to the schedule outlined in Figure 1 (Visit 11).
- Collect samples for clinical laboratory assessments and for storage of serum, plasma and urine for later biomarker research according to the schedule outlined in Figure 1.
- Perform pregnancy test in women of childbearing potential.
- Measure GFR by means of plasma disappearance of non-radioactive iohexol, iGFR at Visit 11.
- Provide a container and instructions for an overnight urine collection whenever an AER measurement is scheduled at the following visit.

In the days immediately after each visit, upon completion of serum creatinine measurements, participants will receive a new batch of study medication by mail from the research pharmacy. Upon receipt of the new tablets, participants will be instructed to immediately mail the pill bottles or the blister packs with the tablets remaining from the previous prescription to the study center for drug accounting and compliance assessment (see 6.1.2). A pre-stamped and addressed envelope will be provided to participants for this purpose.

At some sites the study medication may be dispensed directly to the study participant at a relevant in person study visit or by mail from the site following a relevant in-person or phone study visit.

8.6. End of Intervention (Visit 16)

At the end of the treatment period (Visit 16), the following procedures will be completed for each participant:

- Obtain interval medical history (with special emphasis on CVD events).
- Review of concomitant medications and AEs.
- Review RASB and BP therapy.
- Collect unused study medication and document compliance.

- Measure height, weight and vital signs.
- Inspect for skin rash.
- Conduct a physical exam.
- Perform ECG.
- Collect samples for clinical laboratory assessments as outlined in Figure 1 and for storage for later biomarker research.
- Perform pregnancy test in women of childbearing potential.
- Measure iGFR.
- Provide containers and instructions for 2 overnight urine collections to be made immediately before Visit 17.

Participants will be instructed to stop taking the study medication and to mail the pill bottles or the blister packs with the tablets remaining from the last prescription to the study center if they did not already bring the unused study medication at the visit. The RAS and BP therapy will be continued as before until the closing visit (Visit 17). The importance of coming back in 8 weeks for the closing visit (Visit 17) will be emphasized.

8.7. End of Wash-out Period (Visit 17)

After the end of the treatment period, participants will enter an 8-week wash-out period at the end of which the following procedures will be completed:

- Obtain medical history.
- Review of concomitant medications and AEs.
- Measure height and weight and vital signs.
- Inspect for skin rash.
- Collect samples for clinical laboratory assessments as outlined in Figure 1 and for storage for later biomarker research.
- Perform pregnancy test in women of childbearing potential.
- Measure iGFR.

8.8. RAS blocking and anti-hypertensive therapy after completion of the study

When the participant completes the study, control of the RAS-blocking and anti-hypertensive therapy will be relinquished to the participants' physicians, who will decide whether or not to continue the therapy established during the study. Participants will continue the anti-hypertensive therapy established during the study until they see their physicians.

8.9. Future biomarker studies

Plasma, serum, and urine specimens and DNA will be stored the Advanced Research and Diagnostics Laboratory at the University of Minnesota and the NIDDK Central Repository for possible future studies of biomarkers of kidney disease in diabetes or other diabetic complications. Twelve ml of plasma, 12 mL of serum, and 24 ml of urine will be collected at Visit 4, 11, 16, and 17, with one quarter of the aliquots of each stored at the University of Minnesota and three quarters of the aliquots sent to the NIDDK Central Repository for storage. Ten ml of whole blood will be obtained at Visit 3. This will be used for white blood cell DNA extraction and subsequent storage. Altogether, the stored plasma and serum aliquots will correspond to about 210 ml of blood collected for this purpose over the entire duration of the study. Participants will be allowed to elect to participate in the study while not having any or one or more of these samples stored, if they so choose.

8.10. Early Withdrawal

Unless the participant withdraws consent, all randomized participants will be followed for the full study period (through week 164) and all data will be collected as scheduled.

9. SAFETY ASSESSMENTS

9.1. Demographic Data/Medical History

After collecting a detailed medical history at Visit 1, this information will be updated at each visit through a structured interview, with a special emphasis on skin symptoms and signs such as rash, itching and exfoliation and on pregnancy in females. Participants will be instructed to communicate any change in their health status and intervening hospitalizations to the study coordinator in-between visits. In particular, they will be instructed to discontinue study medication and immediately contact the study coordinator if they develop a suspicious skin rash, swelling of the lips or mouth, arthralgias, and/or jaundice, which may indicate a hypersensitivity reaction to allopurinol. Fever and chills should also be reported but would not require cessation of medication prior to discussion with study personnel.

9.2 Skin exam

The skin of study participants will be examined for the presence of any kind of rash at each in-person visit. Participants will be instructed to carry-out periodical skin self-exams. If skin abnormalities are reported to the study personnel during the phone visits or on any other occasion, participants will be asked to immediately report to the study site, their PCP's office, or other local healthcare facilities for an in-person skin exam. Suspicion of drug allergy or Stevens-Johnson Syndrome SJS would require immediate discontinuation of study medication and dermatologic consultation.

9.3. Vital Signs

Blood pressure and heart rate will be recorded at each in-person visit. BP readings at home will be reviewed during each phone visits; if abnormal values are reported, participants will be asked to visit the study site, their PCP's office, or other local healthcare facilities to have their BP measured.

9.4. Clinical Laboratory Tests

Serum ALT, creatinine and K⁺, and CBC will be monitored and a pregnancy test, if a female of child bearing potential, performed at each visit. Participants who are started for the first time on RAS blockers as part of this study will have their serum K⁺ and creatinine measured at a local laboratory after 2 weeks of full dose RASB treatment (i.e., after Visit 3). HbA1c will be measured at Visits 1, 4, and 7-17. An ECG will be performed at Visits 2, 4, 11, and 16.

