Blood Pressure and Measurements	x	x	(x)	x	(x)		(x)	(x)	(x)	(x)	(x)	x	(x)	(x)	(x)	(x)	x	x
ECG Report		x		x	(x)							x					x	
Physical Exam		x		(x)	(x)							x					x	
Skin Assessment				x	(x)		x	x	x	x	x	x	x	x	x	x	x	x
Eligibility	x			x	(x)	x												
Randomization						x												
Family History				x	(x)													
RAS and BP Med Log		x	x	x	(x)		x	x	x	x	x	x	x	x	x	x	x	x
IGFR Procedure				x	(x)							x					x	x
PERL Study Drug Prescription						x	x	x	x	x	x	x	x	x	x	x	x	
Study Drug Compliance							x	x	x	x	x	x	x	x	x	x	x	
CENTRAL LAB																		
Serum uric acid, serum creat, cystatin C	x		x	x	(x)		x	x	x	x	x	x	x	x	x	x	x	x
Urine ACR/AER	x		x	x	(x)				x		x						x	x
HbA1c	x			x	(x)			x	x	x	x	x	x	x	x	x	x	x
HLA B*58:01				x	(x)													
iGFR				x	(x)							x					x	x
NIDDK Repository: serum, plasma, urine				x								x					x	x
LOCAL LAB																		
Pregnancy test serum HCG	x		x	x	(x)		x	x	x	x	x	x	x	x	x	x	x	x
Pregnancy test urine dipstick		x		x	(x)							x					x	x
ALT, K, CBC, serum creatinine, urine	x		x	x	(x)		x	x	x	x	x	x	x	x	x	x	x	x
Protocol Deviation		x	x	x	(x)		x	x	x	x	x	x	x	x	x	x	x	x
Adverse Events		x	x	x	(x)	x	x	x	x	x	x	x	x	x	x	x	x	x

*If normal blood pressure control is not achieved at Visit 4, the run-in period may be extended for two more weeks after which participants will be examined as in Visit 4 (Visit 4A). In this event, the GFR measurement scheduled for Visit 4 will be conducted at Visit 4A.

^ Study visits will be generally conducted at the Study Sites or their Satellites. "In-Person Visits" (V) are required for Visit 2 and all visits requiring iohexol-GFR measurements. If a participant lives far from a study site or satellite, or travel impediments are present, other (O) visits may be conducted remotely or in-person. For any given study visit to be conducted remotely, a Phone Visit and a Remote Biospecimen Collection will be both required; a Phone Visit is performed by the study coordinator using the telephone or other media such as Skype to collect results of study procedures that do not require physical interactions (e.g., collection of medical history), and a Remote Biospecimen Collection is performed at a clinical laboratory close to where participants live.

Note: (x) indicates an optional assessment For BP and Measurements, (x) indicates an optional assessment only if the patient is NOT seen in-person.

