8.3. Run-in Period (Visits 2, 3, and 4)

Starting at **Visit 2**, eligible subjects who agree to participate in the study will enter a run-in period of 9 weeks (see note at the end of this section for exceptions to this duration). During this visit, subjects will undergo the following procedures:

- Obtain written informed consent to enter run-in period (if the consent at V1 was only for screening).
- Review the fetal risks of RAS blockade.
- Collect medical history.
- Perform ECG.
- Collect concomitant medications.
- Measure weight and height.
- Measure vital signs.
- Physical Examination
- Obtain a urine pregnancy test

RAS antagonist treatment will be standardized, and BP, if elevated (>140/90 mm Hg), normalized. Letters will be written to the participants' physicians informing them about the study and notifying them of the study's protocol RAS blocker requirements and blood pressure goals. The letter will propose active participation of the participants' physicians in blood pressure management with the

availability of advice from the PERL site physicians and, if needed, the PERL Drug monitoring Committee for out of range blood pressure values during the course of the study. The run-in period will start at **Visit 2**. If a participant is already on a RAS Blocker, its dose will be increased, if necessary, to make it at least equivalent to ramipril 10 mg (if on ACE inhibitor [ACEI]) or irbesartan 300 mg (if on an angiotensin receptor blocker [ARB]), if acceptable to the patient's primary physician, if tolerated and if not contraindicated (see below). Participants who were not taking a RAS Blocker will be prescribed and instructed to start taking 10 mg of ramipril daily or 300 mg of irbesartan daily (if ramipril is contraindicated or has side effects) or another ACE inhibitor or ARB at equivalent doses if there are impediments to the use of ramipril or irbesartan. Participants who have contraindications to RAS blockers (e.g., SBP<100 mmHg, K⁺>5.5 mEq) or do not have evidence or history of micro- or macroalbuminuria (as defined in 5.1.4), are normotensive, and are not being treated with RASB or other anti-hypertensive agents will not be treated with these drugs, as this represents the standard of care.

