8.4. Enrollment in the Study and Randomization (Visit 5)

- At the end of the run-in period, eligibility will be re-assessed based on the BP measures obtained at Visits 4 or 4A (if applicable), HLA-based genetic susceptibility to allopurinol skin reactions^{36,37} (tested at Visit 4) and a valid baseline iGFR measurement. Participants who are eligible for randomization based on those measures (SBP ≤ 150 and DBP ≤ 95 mmHg) and a negative HLA B*58:01 test will be telephoned by the study coordinator to discuss how the

study medication should be taken and its potential side effects.

- Immediately after the phone call, the participants will be randomized.
- Immediately after randomization the first batch of study medication will be mailed to the participant by the research pharmacy along with written instructions on how to take it. Participants will be instructed to notify the study personnel by phone and start taking the study medication as soon as they receive it.
- If the participant is positive for HLA-based genetic susceptibility to allopurinol skin reactions, or acceptable BP measurements, or a valid iGFR measurement cannot be obtained, he/she will be discontinued from the study prior to randomization.

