13.5. Procedures for protecting against and minimizing potential risks

a. General

The patients are under constant medical supervision. They are told that the data which are collected will be used for scientific report, but they will not be identified in such reports.

b. Specific

1. Regular pregnancy tests and education regarding fetal risk of the study drug will be provided to female patients of child bearing age.
2. Quarterly measures of liver enzyme and white blood cell count will allow for early detection of liver injury or leucopenia potentially representing drug toxicity.
3. Quarterly measures of serum creatinine will allow titration of allopurinol in relation to kidney function to avoid excessive dosage of the medication.
4. IV's for kidney function studies will be placed by trained skilled clinical research nurses or technicians or by experienced physicians.
5. Blood drawing for laboratory studies will be performed by trained skilled phlebotomy personnel at the respective institutions, thus limiting the risk of discomfort or local hematoma formation.
6. Participants will be advised not to donate blood throughout the time they are in the study.
7. Regarding possible drug toxicity:
 - a. To avoid fetal risks from the study drug, patients planning pregnancies will not be included. Sexually active female patients will be instructed to immediately discontinue study drugs and RAS blockers if a menstrual period is missed by more than two weeks and, if found to be pregnant, the study medication and RAS blocker will be discontinued and not resumed until pregnancy and nursing are completed. Pregnancy tests will be done on all women of child-bearing potential at each visit.
 - b. Subjects with known allergy to xanthine-oxidase inhibitors will be excluded from the study. Patients will be instructed to immediately report skin reactions and allergic symptoms and to immediately stop the study medication should these occur. Patients will be given antihistamines for symptom relief. A small supply of antihistamines to be used in such an event will be supplied to each patient. Should an allergic reaction or skin rash occur, the study drug will be permanently discontinued.

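### The protocol promises a pregnancy test at each visit, but none is scheduled at Visit 5, where women are randomized and sent their first study drug.

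*Protocol*

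**What the plan says.** Two sections of the Protocol make the same unqualified promise. Section 9.4 has "a pregnancy test, if a female of child bearing potential, performed at each visit". Section 13.5 (part b, item 7a) has "Pregnancy tests will be done on all women of child-bearing potential at each visit".

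The schedule in Figure 1 (section 8.1) has two relevant rows, "Pregnancy test serum HCG" and "Pregnancy test urine dipstick". Both are blank at Visit 5. The visit-by-visit lists agree with the figure: sections 8.2, 8.3, 8.5, 8.6 and 8.7 each name a test (for Visit 2, "Obtain a urine pregnancy test"), and section 8.4, which covers Visit 5, names none.

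Figure 1 codes Visit 5 as a phone call. Under section 8.4, "eligibility will be re-assessed based on the BP measures obtained at Visits 4 or 4A (if applicable), HLA-based genetic susceptibility" and a valid baseline iGFR. The participant is randomized straight after the call. "Immediately after randomization the first batch of study medication will be mailed to the participant", and she is told to start on receipt.

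Pregnancy is exclusion 17 in section 5.2. Section 13.4.2, item e, takes a precautionary position because human data are scarce, and treats allopurinol as unsafe for mother and fetus. The back-up in section 13.5 tells sexually active women to "immediately discontinue study drugs and RAS blockers if a menstrual period is missed by more than two weeks".

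**The concern.** Visit 5 is the last point at which fetal exposure to allopurinol can be avoided altogether; every later test can only shorten an exposure that has already begun. It is also the only numbered visit without a test. A woman who conceives after her Visit 4 test can be randomized, receive drug by mail and take it until either the missed-period rule or the Visit 6 test stops her. A blank cell does not forbid a site from testing. But a site that does exactly what 8.4 and Figure 1 ask does not deliver the safeguard stated in 9.4 and 13.5. What is at stake is participant protection and the consistency of the protocol. Type I error, power and the primary estimate are not in question.

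**Working it through.** **Which visits have a test (Figure 1)**

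| Row | Visits marked | Blank at |
|---|---|---|
| Serum HCG | 1, 3, 4, (4A), 6 to 17 | 2, 5 |
| Urine dipstick | 2, 4, (4A), 11, 16, 17 | 1, 3, 5 to 10, 12 to 15 |

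The serum row covers 3 + 12 = 15 numbered visits. The urine row adds Visit 2, giving 16 of 17. Only Visit 5 is blank in both rows. Visit 4A is marked optional.

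**Does another section supply the test?** Section 4.1 includes Visit 5 among the visits that may be done remotely, and says a remote visit needs a biospecimen collection. Figure 1, however, codes Visit 5 as a phone call, not as an in-person-or-remote visit, and schedules no specimen there. So 4.1 does not fill the gap.

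**Age of the last test, on target dates (Figure 1)**

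- Visit 4 is at week −3, Visit 5 at week 0 and Visit 6 at week 4.
- Visit 4 to randomization: 0 − (−3) = 3 weeks. Section 8.3 gives the same figure: a 9-week run-in less 6 weeks to Visit 4 = 3 weeks.
- Visit 4 to the next scheduled test: 4 − (−3) = 7 weeks.
- Time on drug before the next test: at most 4 weeks, less mailing time, at the starting dose of 100 mg/day (section 6.1.2).
- Mailing time, which the protocol does not give, adds to the 3 weeks before first dose.

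**With the visit windows (section 8.1)**

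- Visits 4 and 5 each have ±2 weeks, so Visit 4 can fall at weeks −5 to −1 and Visit 5 at weeks −2 to +2.
- Longest gap: 2 − (−5) = 7 weeks. The windows overlap, so the shortest gap is about 0.
- If Visit 4A is used two weeks after Visit 4, its optional test is done and Visit 5 does not move, the gap is 3 − 2 = 1 week.
- For participants who go directly from Visit 1 to Visit 4, section 8.3 gives no new Visit 5 date, so no interval can be calculated.

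**When the missed-period rule would act**

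The documents do not give the time from conception to the next expected period. Assume 2 weeks, with a range of 1.5 to 2.5. The rule then needs a further 2 weeks of lateness.

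- Conception at week −3: −3 + 2 + 2 = week +1 (range +0.5 to +1.5).
- Conception at week 0: 0 + 2 + 2 = week +4 (range +3.5 to +4.5).

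For any conception between the Visit 4 test and randomization, the rule acts no earlier than about week +1 to +4 (overall range +0.5 to +4.5). On target dates that is after the first shipment.

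**The case against.** The strongest reply is that 9.4 and 13.5 use loose summary wording. The same sentence of 9.4 also covers ALT, creatinine, potassium and CBC, and Figure 1 leaves that row blank at Visit 5 as well. Sites work from Figure 1 and 8.4, which agree, so the repair could be to write an exception for Visit 5 into 9.4 and 13.5. Against this, sections 9.2 and 9.3 limit their checks to in-person visits, so such a limit was written where it was meant. Removing the promise would also leave first dosing on an old test.

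Other points stand in part:

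- **Eligibility.** Figure 1 marks eligibility at Visit 5, so exclusion 17 formally still applies. The mark supplies no test result.
- **Later intervals are longer.** Visits 6 and 7 are 12 weeks apart and most later visits 14 to 16 weeks apart, at 200 to 400 mg/day. This is true, but those tests monitor women already on drug.
- **Few women are affected.** The SAP (section 3.3) gives a median age of 52 years, about half the participants were expected to be men (Protocol 13.1), contraception is required, and women planning pregnancy are not enrolled. The number at risk is probably small, and the documents do not allow an estimate of it.
- **Timing of the remedy.** The February 2017 SAP already gives 530 subjects against a target of 480, and the protocol is dated February 2018. Randomization may have been complete by then, in which case the amendment would act on few or no participants.

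**Conclusion.** The concern holds. Sections 9.4 and 13.5 promise a test at every visit, and the schedule omits it at the one visit that leads directly to first dosing. On target dates the last scheduled result is 3 weeks old at randomization, plus mailing time, and tests are 7 weeks apart across the start of drug. The windows allow a test-to-randomization gap of about 0 to 7 weeks. These figures describe the standard run-in and take randomization to fall on the Visit 5 date; SAP section 3.4 notes that the two dates need not coincide. The missed-period timing rests on the assumed 2 weeks (1.5 to 2.5) from conception to expected period. The number of women exposed is likely to be low, but the exposure is avoidable. The protocol should be changed, although the validity of the trial's result does not depend on it.

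**What to change.** Add to section 8.4, and to the Visit 5 column of Figure 1, a new negative pregnancy test for women of child-bearing potential, with the result known before the first shipment is released. List that result with BP, HLA B*58:01 and iGFR in the Visit 5 eligibility re-assessment. The test can be done at the site, as a home urine test, or through the remote collection in section 4.1, which already covers pregnancy tests. If randomization is complete, correct the text and report the actual interval from last test to first dose.

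The cost is one inexpensive test per woman concerned, a possible short delay to the first shipment, and small edits to 8.4 and one column of Figure 1. The analysis and sample size do not change. Some risk remains, because a test at Visit 5 cannot detect a very recent conception and mailing time still follows it.

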9.5. Management of Uric Acid Levels

Study participants and study personnel, other than the DCC and the study pharmacists, will be masked as to the uric acid levels obtained during the study. The patients' physicians will receive written requests to refrain from measuring uric acid levels during the time of the patients' participation in the study, except as is mandatory for the patient's wellbeing, e.g., in the treatment of malignancy or diagnosis of a clinical syndrome highly likely to represent gout. If gout is diagnosed, open-label treatment with allopurinol will become indicated. In such case, the study drug will be discontinued but the patient will remain in the study and will continue to be followed as if he/she was taking the study medication. If uric acid lowering for malignancy treatment is required, the patient will receive open-label treatment until such time as return to study drug is deemed clinically reasonable by their physician.

